### **6.3.12 Other Laboratory Studies**

Blood will be collected for cellular biomarkers at Screening, 2, 8, 10, and 16 month visits (visit 1, 5, 9, 11, and 14). Biomarkers to be analyzed will include ERK, AKT, S6 kinase, APP, and MMP9. DNA and plasma leftover from the 3 ml samples noted above will be banked for future studies related to FXS.

If the biomarker blood samples cannot be collected at the screening visit, sites may collect them at the -2 month or baseline visits (v2 or v3) as long as it is prior to randomization. If the biomarker blood samples cannot be obtained at a visit occurring post-randomization (v5, 9, 11 and 14), then the samples may be collected at the next visit to the site.

Blood will also be obtained (as possible) for RNA and protein banking at Screening, 2, 6, 10, 16 month visits (visit 1, 5, 9, 11, and 14). Every attempt will be made to get blood for biomarkers

from all subjects, however this will be challenging due to the volume of blood to be obtained. Biomarker samples are expected to be able to be obtained from at least 75% of subjects. Processing and shipping of blood samples for biomarkers and banking will be done according to procedures described in the Study Lab Manual. Materials for sample collection, processing and shipping (not including Fed Ex labels and account number) for the biomarkers will be provided to the study sites by the PPI site.

ELISA will be utilized for measuring APP levels. The sandwich ELISA for APP will use antibodies immobilized in a microtiter plate that bind to target antigens consisting of total APP, APP alpha or APP beta, after an overnight incubation with plasma samples from participants. A specific detection antibody against a different epitope of either of the APP proteins is used to form a complex that will be detected after addition of a chromogen reagent. The fluorescence signal will be detected at 450 nm immediately after addition of a stop solution. An Illuminex assay will be used for measuring MMP9 levels. The Illuminex assay will use a mixture of specific antibodies, each bound to a magnetic microsphere or bead that will allow the simultaneous measurement of MMP9 and MMP2 in the samples from participants. The unbound beads will be washed out and a labeled secondary antibody added. The complex will be detected by addition of a Streptavidin-PE conjugate that acts as a reporter molecule when the microspheres are excited using lasers. The fluorescent signal will be digitally recorded for each MMP9 and MMP2. Expression levels of ERK-S6K and AKT (total and phosphorylated forms) will be measured by Western Blot analysis as described in Hoeffer et al.. Biomarker data will be sent to the NeuroNEXT DCC via an established data transfer mechanism. These values will not be visible to the sites to avoid potential unblinding.

### 6.3.13 Questionnaires

#### **MacArthur-Bates Communicative Development Inventory**

The MacArthur-Bates Communicative Development Inventory (Words and Sentences version) will be administered at Screening, AFQ Baseline and 2, 4, 6, 8, 12, 16 month and Follow Up visits (visit 1, 3, 5, 7, 8, 9, 12, 14, and 15) to follow language development. This assessment can be administered by a Coordinator, Psychologist or Speech and Language Pathologist. The assessment consists of two parts: a) Part 1 (Words Children Use) is a 680-word vocabulary checklist in which the parent indicates those vocabulary words the child regularly produces in spoken language; and, b) Part 2 (Sentences and Grammar) assesses several aspects of grammar and word endings. This parent-report measure has been well-validated against direct observation and assessment measures of child language status and growth. Test booklets with scores will be maintained with the source documents. Parents will use the same test protocol at each time point using different color ink to indicate newly acquired words or grammatical constructions. Raw scores for each time point will be computed and recorded in the source documents and entered in the CRFs.

The MacArthur Bates Communicative Development Inventory should be administered by the same rater for a given subject at all applicable visits throughout the trial. The parent/legal guardian completing the assessment with the study staff member should also remain the same at all applicable visits throughout the trial. If the same rater cannot administer the assessment and/or the same parent/legal guardian cannot complete the assessment, the site must contact the Study Team prior to proceeding and/or scheduling.

**Administration time:** Caregiver completes independently at own pace, but typically requires no more than 45 minutes.

**The Vineland Adaptive Behavior Scales, Third Edition (Vineland-3)** will be administered as an interview to a parent/caregiver by trained study staff authorized to perform the interview at Screening, AFQ Baseline and 2, 4, 6, 8, 12, 16 month and Follow Up visits (visit 1, 3, 5, 7, 8, 9, 12, 14, and 15). This assessment can be administered by a Coordinator, Psychologist or Speech and Language Pathologist.

The Vineland-3 is a valid and reliable measure of a person's adaptive level of functioning from birth to 90 years of age. It is commonly used in clinical care and research to measure the development and functioning of individuals with and without disabilities, including studies of natural development and clinical trials in FXS. The Vineland is an informant-based measure that yields an adaptive behavior composite score and domain standard scores in domains of: Communication (receptive, expressive, and written adaptive language functions), Daily Living Skills (personal, domestic, and community skills), Socialization (interpersonal relationships, play and leisure time, and coping abilities), and Motor Skills (gross and fine motor skills). This structure corresponds to the three broad Domains of adaptive functioning recognized by the American Association of Intellectual and Developmental Disabilities .

The Survey Interview Edition will be administered to parents or caregivers using a semi-structured interview format. Interview booklets with raw and standard scores should be maintained in the source documents at the site if utilized; alternatively, the Q-global application can be used during the assessment to input responses directly into the system. Sites should use the Q-global application to calculate the composite and individual domain scores, and produce a score report. The score report must be printed from the Q-global application and filed in the subject's binder. The composite standard score and all Vineland-3 domain raw and standard scores will be entered into the CRFs.

The Vineland-3 should be administered by the same rater for a given subject at all applicable visits throughout the trial. The parent/legal guardian completing the assessment with the study staff member should also remain the same at all applicable visits throughout the trial. If the same rater cannot administer the assessment and/or the same parent/legal guardian cannot complete the assessment, the site must contact the Study Team prior to proceeding and/or scheduling.

The Vineland-3 can be administered via phone following completion of the study visit if there is not enough time to complete the assessment during the visit.

Administration time: 45-60 minutes with caregiver.

**Visual Analog Scale (VAS) for Language and Communication** will be completed at Screening and all subsequent study visits (visits 1 – 15). In an attempt to measure the general level of language difficulty experienced by the parent/caregiver with respect to the child with FXS, the VAS will allow parents to mark on a visual line measuring 100 mm with one side marked “worst language/communication” and the other side marked “best language/communication for age”. Families will rate the subject's overall language/communication which will include receptive language and non-verbal communication as well as expressive language. The vertical marks are measured in millimeter distance where they fall from the “worst language” side (left end of the line) so that improvements or worsening of language/communication over the treatment period can be evaluated. The VAS has been successfully used in a FXS-specific clinical trial. Copies of the VAS with lines and measurements will be kept in the source documents. Scores in terms of centimeter distance

from the “worst language” end of the line will be recorded in the source documents and entered into the CRFs.

The VAS for Language and Communication should be administered by the same rater (parent/legal guardian) for a given subject at all applicable visits throughout the trial. If the same rater cannot administer the assessment, the site must contact the Study Team prior to proceeding and/or scheduling.

Administration time: 5 minutes for caregiver.

**The Aberrant Behavior Checklist- Community Edition (ABC) scored using the FXS-specific factoring system (ABC-FX)** will be completed by the parent/caregiver at Screening, AFQ Baseline and 2, 4, 8, 10, 12, 16 month and Follow Up visits (visit 1, 3, 5, 7, 8, 9, 11, 12, 14, and 15). This parent/caregiver report measure is the gold standard measure of problem and interfering behaviors in clinical trials in DD.

The ABC is actively used in over 70 countries and has been translated into over 30 languages including Spanish. The ABC asks responders to rate behaviors from 0 “not a problem at all” to 3 “the problem is severe in degree” across 58 questions. Its use has been validated in a variety of clinical populations, including in ASD and FXS, has been used extensively in clinical trials, and is a FDA-vetted endpoint utilized in the FDA approvals for use of risperidone and aripiprazole targeting irritability in youth with ASD. It has been subjected to utility analysis in FXS and linked to caregiver stress in families.

Scores will be analyzed using the FXS-specific factor structure such that 54 of the items resolve into 6 subscales (Irritability, Lethargy, Social Avoidance, Stereotypic Behavior, Hyperactivity, and Inappropriate Speech). Questionnaires with raw data and the six FX-factor subscale scores will be kept in the source documents. Scores for the six FX-specific factors will be recorded in the CRFs.

The ABC-FX should be administered by the same rater (parent/legal guardian) for a given subject at all applicable visits throughout the trial. If the same rater cannot administer the assessment, the site must contact the Study Team prior to proceeding and/or scheduling.

Administration time: 10-15 minutes for caregiver

**Visual Analog Scale (VAS) for Behavior** will be completed at Screening and all subsequent study visits (visits 1 – 15). In an attempt to measure the general level of behavioral difficulty experienced by the parent/caregiver with respect to the child with FXS, the VAS will allow parents to mark on a visual line measuring 100 mm with one side marked “worst behavior” and the other side marked “best behavior”. Families will pick and rate the subject’s three behaviors. The vertical marks are measured in millimeter distance where they call from the “worst behavior” side (left end of the line) so that improvements or worsening of behavior over the treatment period can be evaluated. The VAS has been successfully used in a FXS-specific clinical trial. Copies of the VAS with lines and measurements will be kept in the source documents. Scores in terms of centimeter distance from the “worst behavior” end of the line will be recorded in the source documents and entered into the CRFs.

The VAS for Behavior should be administered by the same rater (parent/legal guardian) for a given subject at all applicable visits throughout the trial. If the same rater cannot administer the assessment, the site must contact the Study Team prior to proceeding and/or scheduling.

Administration time: 5 minutes for caregiver.

**Children's Sleep Habits Questionnaire (CSHQ)** will be completed at Screening, AFQ Baseline, 1, 2, 8, 9, 10, and 16 month and Follow Up visits (visits 1, 3, 4, 5, 9, 10, 11, 14, 15). The CHSQ is a parent report, sleep screening instrument that has been used in FXS to characterize sleep problems in the population, and which will be utilized to screen for the presence and impact of sleep problems that may occur as a side effect of AFQ056.

The CSHQ should be administered by the same rater (parent/legal guardian) for a given subject at all applicable visits throughout the trial. If the same rater cannot administer the assessment, the site must contact the Study Team prior to proceeding and/or scheduling.

Administration time: 10 minutes for caregiver.

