Adverse events seen in the prior adolescent and adult placebo-controlled studies of AFQ056 in FXS more frequently in the group treated with AFQ056 than with placebo include the following list arranged in alphabetical order. No side effect exceeded a frequency of 20%, even at the highest doses of AFQ056 (see section 2.2 above for exact frequencies). In the Pediatric PK study, side effects all fell into the below categories, with vomiting and insomnia being the most frequent side effects. These were typically short-lived occurring in the first day or two of dosing and seemingly related to advancing to the full dose right from the outset of doing rather than titrating the dose up over time. This was evident in that vomiting after the initial dose was seen in 50% of the 5-11 year old cohort studied first all of whom were dosed from the outset at the full dose, but not seen in the 3-4 year old cohort after dosing was advanced over the course of a day (half dose for one day, followed by the full dose).

- Abdominal pain
- Agitation
- Aggression
- Anxiety
- Decreased appetite
- Diarrhea
- Dizziness
- Fatigue
- Headache
- Insomnia
- Irritability
- Nausea
- Pyrexia
- Self-injurious behavior
- Vomiting

Although not seen in prior trials in humans with FXS, including after AFQ056 exposure for over two years in the open-label extension studies with adults and adolescents (2278 and 2279), learning and memory impairment have been noted in preclinical testing of AFQ056. Learning was, however, enhanced in preclinical testing in the FXS mouse model, presumably due to the AFQ056 targeting the abnormal signaling pathway in the FXS mouse. Risk of learning and memory impairment will be monitored closely using assessments that are being administered as part of the protocol. Raw scores on the MSEL and VABS-II assessments will be monitored at the sites to assess global developmental functioning. If there is a decrease in raw scores on both measures by 10% incrementally at two consecutive visits where both assessments are administered (e.g. 10% decrease from screening to baseline, baseline to month 2, month 2 to month 8, or month 8 to month 16 as described in the schedule of assessments), subject data will be reviewed by the Medical Monitor and it will be decided if the subject should be withdrawn from the study. If there is decrement in these scores without any obvious alternative cause the participant will be withdrawn from the study.

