### **9.5.2 Key Secondary Outcome(s)**

**Functional Key Secondary Outcomes:** One key secondary objective of this study is to show greater improvement in specific standardized language, cognitive, and adaptive measures (see Endpoints Derived from Evaluations Section). To address this objective, a number of key secondary functional endpoints will be obtained (using all raw scores, except as noted):

- Mullen Scales of Early Learning (MSEL)
  - Development Quotient (DQ)
  - Expressive Language Subscore
- Vineland Adaptive Behavior Scale – Version 3
  - Composite Score
  - Communication Subscore
- Preschool Language Scale – 5th Edition
  - Expressive Communication Score
- McArthur-Bates Communication Development Index
  - Number of Spoken Words
- Clinical Global Impression-Improvement (CGI-I)
  - Overall Function

Although the primary outcome was chosen to be the likely most sensitive measure to the intervention, albeit less validated, the additional key secondary functional outcomes were chosen to be the measures most validated, accepted and utilized in the FXS population, albeit potentially somewhat less sensitive to change. This should allow exploration of both novel and sensitive strategies for measuring outcome as well as standard strategies. The secondary measures chosen will most reliably assess broad domains of cognitive, language, adaptive and maladaptive functioning. It is anticipated that gains in language will result in broader improvement in overall functioning in multiple domains, and it is possible the AFQ056 will target learning in domains outside of those covered by the language intervention, although it is hard to predict which domains will be most impacted. Thus, the mostly broadly used and well-validated general standardized measures for the cognitive, language, adaptive and maladaptive domains were chosen as key functional secondary outcomes.

The Mullen Scales of Early Learning (MSEL) has been used to track developmental progress of children with FXS in longitudinal studies and to characterize cohorts of young children with FXS for many years. More recently the MSEL was analyzed in a retrospective chart review to evaluate effects of early sertraline treatment on development in FXS and has been used in a 6 month placebo-controlled clinical trial of sertraline in young children with FXS.

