### **9.6.2 Key Secondary Hypotheses**

For the key secondary hypotheses, a high level statistical analysis plan is described below. Further details and specifications regarding the assessment of each hypothesis will be provided in a formal statistical analysis plan prior to data lock.

**Functional Key Secondary Hypotheses:** *Children treated with AFQ056 will show greater normalization of specific measures of language and one or more other domains (including cognitive, adaptive behavior, global functioning based on change from baseline (visit 3 assessment) to 8 months (visit 9 assessment) than those treated with placebo.*

All of the key secondary functional outcomes are measured on scales similar to that of the weighted communication score primary outcome. All key secondary functional hypotheses generally state that there will be greater improvement in language, communication, cognitive, developmental, and adaptive functioning in the AFQ056-treated group over the placebo group during an 8-month period [baseline (visit 3 assessment) to 8 months (visit 9 assessment)]. Each scale produces a numeric score that can be assessed in a manner similar to that described for the assessment of the primary endpoint in section 9.6.1.

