- Longitudinal analysis to determine whether the rate of change in language, functional, or biomarker responses in the group assigned to placebo will be lowest during the first 6 months of the study (Screening to visit 5/month 2), higher in the next 6 months with the language intervention (visit 5/month 2 to visit 9/month 8), and highest in the final 8 months with both the language intervention and AFQ056 treatment (visit 9/month 8 to visit 14/month 16) – with inflection points at visit 5/month 2 when the language intervention is started and visit 9/month 8 when AFQ056 is started.
- Analyses of change from baseline at the 2 month visit (visit 5) will be evaluated for all clinical and biomarker outcomes, to determine if effects of drug alone can be identified before the language intervention is initiated. Likewise analyses of change from baseline and from the final visit before weaning treatment with AFQ056 (16 month visit, visit 14) at the Follow Up visit (visit 15) will be evaluated for all clinical and biomarker outcomes, to determine if regressive effects of coming off drug are evident. Covariates in the analyses will be medication (coded as a factor with a small number of levels), age, and additional variables that are shown to be imbalanced through unlucky randomization.

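### Followed as written, the CDI spoken-word count is a cumulative tally: loss of words already ticked is hidden, so the CDI part of the visit-15 off-drug analysis cannot show regression.

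*Combined protocol and SAP*

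**What the plan says.** Section 9.5.2 lists the CDI outcome "Number of Spoken Words" among the key secondary functional endpoints. Section 6.3.13 describes Part 1 of the form as measuring a current state: it "is a 680-word vocabulary checklist in which the parent indicates those vocabulary words the child regularly produces in spoken language".

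For repeat administrations, the same section says: "Parents will use the same test protocol at each time point using different color ink to indicate newly acquired words or grammatical constructions". It continues: "Raw scores for each time point will be computed and recorded in the source documents and entered in the CRFs". The schedule covers nine administrations, given as "Follow Up visits (visit 1, 3, 5, 7, 8, 9, 12, 14, and 15) to follow language development", so it includes the off-drug visit 15.

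Two analyses use the score. Section 9.6.2 carries the primary-endpoint method over to the key secondaries: "Each scale produces a numeric score that can be assessed in a manner similar to that described for the assessment of the primary endpoint". That method is a linear mixed model for the difference in slopes, and the key secondary hypotheses run from visit 3 to visit 9. Section 9.6.3 adds change at visit 15, from baseline and from visit 14, for all clinical and biomarker outcomes, "to determine if regressive effects of coming off drug are evident".

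Section 7 explains why loss is of interest at all: "learning and memory impairment have been noted in preclinical testing of AFQ056".

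**The concern.** The definition of the checklist and the way it is filled in do not match. A count of words now in regular use can rise or fall. A single booklet to which new ticks are added in a new ink can only rise or stay level unless someone also strikes old ticks, and no passage asks for that. A word that was truly used and later lost, or that was ticked by mistake, is counted at every later visit. The parent also sees all earlier answers each time.

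The plan then asks this score a question about loss. If vocabulary is lost after drug is stopped, the visit 14 to 15 change on the CDI will still be zero or positive. A null finding there would be a product of the form, yet it could be reported as evidence of no regression. During the placebo-controlled period, a difference between arms in loss of words already ticked would also go unseen.

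**Working it through.** The documents state no power, variance or expected change for the CDI, so there is no plan figure to reproduce. The check is a logical step, followed by an illustration on assumed rates.

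**Step 1: scoring rule as written.** Let S(v) be the raw score at visit v and N(v) the words newly ticked at v. With one booklet and no rule for removing ticks, S(v) = S(previous visit) + N(v), with N(v) ≥ 0. Hence S(9) − S(3) ≥ 0 and S(15) − S(14) ≥ 0 for every child. The quantity defined in 6.3.13 is instead C(v) = C(previous visit) + gained − lost, which can fall.

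**Step 2: what still shows.** If drug slows acquisition, N(v) is smaller and the slope of S is lower, so the slope comparison can detect slowing. Only the term for lost words is missing from S.

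**Step 3: visit 14 to 15 (assumed figures).** Take 200 words ticked at visit 14, with 20 lost and 5 gained by visit 15.
- Current words: 200 − 20 + 5 = 185, change −15.
- Reused booklet: 200 + 5 = 205, change +5.

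With no gain and 5% to 20% of words lost, the true change is −5 to −20 from 100 words and −15 to −60 from 300 words. The recorded change is 0 in every case.

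**Step 4: visit 3 to 9 (assumed rates).** The CDI is given at visits 3, 5, 7, 8 and 9, which is four steps. Of 680 items, let g = 2% of unknown words be gained and a fraction l of known words be lost per step. The expected current count follows C(next) = C(1 − l) + (680 − C)g. The reused form gains (680 − C0)(1 − 0.98^4) = (680 − C0) × 0.0776, whatever l is.

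| Baseline C0 | Loss per step | Change in current words | Recorded change, reused form |
|---|---|---|---|
| 50 | 0% | +49 | +49 |
| 50 | 10% | +25 | +49 |
| 200 | 0% | +37 | +37 |
| 200 | 2.5% | +17 | +37 |
| 200 | 5% | −1 | +37 |
| 200 | 10% | −35 | +37 |
| 400 | 0% | +22 | +22 |
| 400 | 10% | −115 | +22 |

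For C0 = 200 and l = 10%, the expected counts are 200, 189.6, 180.4, 172.4 and 165.3, a change of −34.7. An item-level simulation of 2,000 children per scenario agreed with these expectations to about 0.3 word, and no child had a negative recorded change.

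**Step 5: effect on the arm comparison (assumed SDs).** Suppose the arms differ only in loss, by 20 words on average, with 50 children per arm and a simple two-sample comparison of change. On a form re-rated at each visit, two-sided 5% power is 0.92, 0.38 or 0.20 for an SD of 30, 60 or 90 words. On the reused form the expected difference is 0, so the rejection rate stays near the nominal level.

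**The case against.** Several points on the other side are sound.

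- **Silence is not prohibition.** Section 6.3.13 does not say that parents mark new words and nothing else, nor does it forbid crossing a word out. Staff administer the form, and the Manual of Operations is not available here. A reader might infer that the score can never fall. The documents support only the narrower statement that it cannot fall under the procedure as written. If some families strike words unprompted and others do not, the score becomes a mixture of two definitions.
- **Slowing is visible.** A reader might infer that the endpoint is blind to any harm to vocabulary. It is not: slower acquisition lowers the slope that section 9.6.1 targets.
- **The safety check does not use the CDI.** A reader might infer that monitoring for learning impairment is weakened. Section 7 bases that check on Mullen and Vineland raw scores, so it is untouched.
- **Other measures can fall.** At visit 15 the weighted communication score, the Vineland-3 and the language VAS carry no such marking rule, and the visit-15 analysis is exploratory.
- **True loss may be rare.** Section 2.1 attributes falling standard scores in fragile X to slow progress, not lost skills, and section 7 says learning impairment was not seen in earlier human trials in this syndrome. This leaves the size of any loss unknown. It does not answer the point, because section 9.6.3 sets out to look for regression and this score could not show it.

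**Conclusion.** The point holds in a limited form. Under the stated procedure the key secondary word count is a running total of words ever ticked, not the number now in regular use. Its visit 3 to 9 comparison is insensitive to loss of ticked words, and its share of the visit-15 off-drug analysis cannot give a positive result. A mistaken tick made before visit 3 cancels out of later change scores; one made after visit 3 inflates them.

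The defect is confined to the CDI. The primary endpoint, the sample size and the section 7 safety check are not affected. The logical result needs only one assumption: that sites follow section 6.3.13 as written, with no strike rule elsewhere. How many words are hidden cannot be drawn from the documents. Every loss rate, gain rate, baseline count and SD above is an assumption, and the bias is zero if no ticked word is lost and none is ticked in error.

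**What to change.** **Where only cumulative scores exist:** label the endpoint 'cumulative words ever reported', state that it cannot decline, and drop the CDI from the visit-15 regression analysis. This costs a few lines in the analysis plan. It is likely to be the main remedy in this trial: the Synopsis closes enrollment at the end of February 2020 and this version is dated 02/03/2021. With 4 + 8 = 12 months from screening to visit 9, nearly all visit-9 forms would already have been collected.

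**For any series not yet started, or any reuse of the design:** in 6.3.13, have the parent re-rate every word at each visit, either striking in that visit's colour those no longer produced or using a clean checklist. Score the words currently produced.

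**Do not mix cumulative and re-rated scores in one analysis.** Changing the marking rule partway through a child's series would create an artificial drop at the changeover.

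The cost of re-rating is some extra parent time at up to nine administrations of a 680-item list and slightly more visit-to-visit noise than a running total. Section 6.3.13 gives 45 minutes as the usual upper limit for completing the form; whether full re-rating fits within that is not shown.
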